Comparison of the ID NOW and Accula Point-of-Care Assays for the Detection of SARS-CoV-2

[name]. D (ABMM)
Ascension Michigan Laboratory Services
Clinical Microbiology Laboratory

Background:

In December 2019, a novel coronavirus was found to cause respiratory infections in Wuhan Province, China. The virus rapidly spread throughout Wuhan Province, then to other parts of China and eventually the world. The illness ranged from asymptomatic carriers to acute respiratory distress (ARDS). The virus was subsequently named SARS-CoV-2 and the respiratory disease, coronavirus disease-2019 (COVID-2019). In March 2020 the World Health Organization (WHO) classified COVID-2019 as a pandemic (4).

In response to the pandemic, the Food and Drug Administration (FDA) approved several platforms under emergency use authorization (EUA). These platforms do not have full FDA approval and may be used for COVID-19 testing temporarily in a clinical laboratory until the manufacturer receives full FDA clearance for use in the U.S (3).

Two point of care (POC) platforms with current EUA approval are the ID NOW COVID-19 (Abbott) and the Accula SARS-CoV-2 tests (Mesa Biotech) (1,2). Both tests are designated as CLIA waived complexity. POC's play a vital role in the diagnosis of COVID-19, especially in laboratories and clinics where testing including molecular assays and serology is not available.

The ID NOW COVID-19 test is an automated qualitative assay that is EUA approved for use on nasal, nasopharyngeal (NP), and oropharyngeal specimens (2). This assay utilizes isothermal nucleic acid amplification technology for the qualitative detection of SARS-CoV-2 viral nucleic acids within 15 minutes. The Accula SARS-CoV-2 test is also a qualitative assay and is approved for use on nasal specimens. The test uses reverse-transcription polymerase chain reaction followed by lateral flow and provides results within 30 minutes.

Currently the Clinical Microbiology Laboratory at Ascension Michigan Laboratory Services has validated and utilizes the ID NOW COVID-19 assay to analyze Ascension St. John (ASJ) emergency department (ED) and inpatient specimens. While this assay has a high positive predictive value, the sensitivity and negative predictive value are low. Furthermore, acquisition of test kits is limited due to large demand and limited supplies.

Purpose:

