The purpose of this study is to compare SARS-CoV-2 results from clinical specimens on the ID NOW and the Accula systems. If the Accula system is comparable or demonstrates superior test parameters including sensitivity, then this assay may potentially be used throughout Ascension, especially in markets which have limited access to testing. This in turn will assist in improving turnaround times for COVID-19 results and facilitate reinstating elective surgeries.

Methods:

All testing will be conducted in a College of American Pathologists (CAP)- accredited biosafety level-2 laboratory with restricted access. All patient specimens will be manipulated under a certified biosafety level-2 cabinet.

The testing personnel for the ID NOW will be medical laboratory technologists and technicians in the clinical microbiology laboratory who have previously been trained and are competent under Clinical Laboratory Improvement Amendments (CLIA) guidelines at performing the ID NOW COVID-19 assay. Testing personnel for the Accula assay will consist of a lead medical laboratory scientist and the technical director of the microbiology laboratory, a Ph.D. level scientist.

The ASJ microbiology laboratory validated the ID NOW COVID-19 assay in April 2020. The protocol for testing is located on PolicyStat and can be accessed using the link below. https://ascension-lab.policystat.com/policy/7897941/latest/. Currently when rapid COVID-19 tests are ordered on ASJ ED patients or inpatients one nasal swab is collected by the clinical staff. The swab is then placed in a sterile conical tube and delivered to the microbiology laboratory where the COVID-19 test is run STAT on the ID NOW. Specimens used for ID NOW testing cannot be re-used for repeat ID NOW testing or any other laboratory testing due to the initial genomic extraction step which requires use of the entire swab.

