If there is a discrepancy between the ID NOW and Accula test results, an additional specimen (nasal) will be collected from the patient, if possible (i.e. if the patient remains in-house) to confirm the COVID-19 results (unless the PCR results are already available). This additional test must be more sensitive than POCs. If the ASJ molecular laboratory is able to complete validation on the Roche 8800 which will be arriving on April 24, 2020, the additional specimen will be run with the Roche COVID-19 assay. If not, specimens will be sent out to a reference laboratory for confirmation COVID-19 testing.

This study will evaluate accuracy (correlation) by comparing Accula results to the ID NOW, precision (reproducibility) by repeating select specimens with different users and on different analyzers, limit of detection by diluting commercial SARS-CoV-2 controls with a known concentration and cross-reactivity by testing known respiratory viruses (including influenza A, B and RSV) on the Accula.

Data Management and Analysis:

The electronic data from this study will be stored on the Ascension network which is a password-protected encrypted computer drive. All HIPAA guidelines will be followed to protect patient information. Only the lead technologist and technical director will have access to this file.

Currently, patient results from the ID NOW test are entered in the laboratory information system (LIS) by microbiology staff. Since the ID NOW is not interfaced with the LIS, patient reports are printed prior to verification and the hardcopies are stored in a binder in the laboratory. As required by CAP, these documents are stored securely in the laboratory for two years.

The lead technologist or technical director will enter the ID NOW results into the secure data file using the ID NOW hardcopy reports. The results from the Accula test and the Roche or send-out test, if performed, will be entered into the same spreadsheet using the same barcode number as the ID NOW. The only patient demographic information that will be recorded in the spreadsheet is the specimen barcode number for the ID NOW.

Any subsequent data shared with individuals other than the study testing personnel will not contain any patient identifiers, including the specimen barcode used as the identifier in the data collection file.

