The following test parameters for the Accula will be calculated using the ID NOW as a comparator: sensitivity, specificity, positive-predictive value, negative predictive value.

Sample Size and Duration of Study:

The aim is to test 100 unique patients. The duration of this study will be determined based upon the number of specimens collected daily. We anticipate that sufficient specimens will be collected within a one-week time period.

Predicted Results:

The Accula SARS-CoV-2 test parameters including sensitivity, specificity, positive-predictive value, and negative predictive value will be similar or superior to the ID NOW COVID-19 assay.

References:

- 1. Accula SARS-CoV-2 Test IFU (EUA). Mesa Biotech, 2020.
- 2. ID NOW COVID-19 Assay IFU (EUA). Abbott, 2020.
- 3. Interim Guidelines for Collecting, Handling, and Testing Clinical Specimens from Persons for Coronavirus Disease 2019 (COVID-19). CDC. Last accessed 20 April 2020.
 - https://www.cdc.gov/coronavirus/2019-ncov/lab/guidelines-clinical-specimens.html
- 4. Laboratory testing for 2019 novel coronavirus (2019-nCoV) in suspected human cases: Interim guidance. World Health Organization. 19 March 2020.

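### Accula is scored against ID NOW, which the plan itself calls insensitive, so it cannot be shown superior; the PCR on discordant pairs, which could show it, has no role in the analysis

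*Combined protocol and SAP*

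**What the plan says.** The plan is one combined protocol and SAP. These statements bear on the point:

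- **Background**, on ID NOW: "the sensitivity and negative predictive value are low". The same sentence credits it with a high PPV. No figures are given.
- **Purpose**, on wider use of Accula: "If the Accula system is comparable or demonstrates superior test parameters including sensitivity".
- **Methods**, on accuracy: "This study will evaluate accuracy (correlation) by comparing Accula results to the ID NOW".
- **Methods**, on discrepant results: "an additional specimen (nasal) will be collected from the patient, if possible (i.e. if the patient remains in-house) to confirm the COVID-19 results", with the exception "unless the PCR results are already available". The confirmatory test has to be more sensitive than the two point-of-care assays.
- **Data Management and Analysis**: "The results from the Accula test and the Roche or send-out test, if performed, will be entered into the same spreadsheet". On the calculation itself: "The following test parameters for the Accula will be calculated using the ID NOW as a comparator", followed by sensitivity, specificity, PPV and NPV.
- **Predicted Results**: the four Accula parameters "will be similar or superior to the ID NOW COVID-19 assay".

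Methods also enrols patients already known to be PCR-positive and swabs them for both assays. No section says how any PCR result enters an estimate or comparison. No accuracy figure for ID NOW is planned against any other reference.

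**The concern.** The aim and the calculation do not fit. The aim is to learn whether Accula is comparable to or better than an assay that misses infections. The calculation treats that assay as the truth, so its misses become Accula's errors. The better Accula is at finding what ID NOW misses, the worse its specificity and PPV look. An Accula that shares ID NOW's misses looks perfect.

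Possible wider use of Accula is tied to this result. The discordant pairs with a PCR result hold the information on which assay is better. They will be collected anyway, but the plan does not say how to analyse them or what to do when the patient has left and no PCR is obtained. A lesser gap is that an already available PCR may be used whatever its age.

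**Working it through.** **Inputs.** From the plan: 100 patients, ID NOW as reference, ID NOW sensitivity low. The plan gives no infected share, sensitivities or overlap of errors, so these are assumed: 40 infected and 60 uninfected, ID NOW true sensitivity sI = 75%, both specificities 100%. The plan derives no figure on this point that could be reproduced first.

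Write A for Accula and I for ID NOW. With I as reference:

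- sensitivity = (A+I+) / all I+
- specificity = (A−I−) / all I−
- PPV = (A+I+) / all A+
- NPV = (A−I−) / all A−

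**1. Error-free Accula against a copy of ID NOW.** ID NOW is positive in 40 × 0.75 = 30 and negative in 70.

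| Accula | A+I+ | A+I− | A−I+ | A−I− | Sens | Spec | PPV | NPV |
|---|---|---|---|---|---|---|---|---|
| Error-free | 30 | 10 | 0 | 60 | 100% | 60/70 = 85.7% | 30/40 = 75.0% | 100% |
| Copy of ID NOW (true sensitivity 75%) | 30 | 0 | 0 | 70 | 100% | 100% | 100% | 100% |

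The exact 95% intervals for the error-free Accula are 75.3% to 92.9% (specificity) and 58.8% to 87.3% (PPV). With D infected among N, its apparent PPV is D·sI / D = sI at any prevalence, and its apparent specificity is (N − D) / (N − D·sI).

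- sI = 60%: PPV 60%, specificity 60/76 = 78.9%.
- sI = 90%: PPV 90%, specificity 60/64 = 93.8%.
- Over 20 to 50 infected and sI of 70% to 90%, specificity runs from 50/65 = 76.9% to 80/82 = 97.6%.

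**2. Imperfect Accula, true sensitivity 80%.** The result depends on how the two assays' misses overlap. True specificity and PPV are 100%, and true NPV is 60/68 = 88.2%.

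| Overlap of misses | A+I+ | A+I− | A−I+ | A−I− | Sens | Spec | PPV | NPV |
|---|---|---|---|---|---|---|---|---|
| Independent | 24 | 8 | 6 | 62 | 80% | 88.6% | 75.0% | 91.2% |
| Midway | 27 | 5 | 3 | 65 | 90% | 92.9% | 84.4% | 95.6% |
| Nested | 30 | 2 | 0 | 68 | 100% | 97.1% | 93.8% | 100% |

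Specificity and PPV are understated. Sensitivity can be overstated by 20 points and NPV by up to 11.8 points (100 − 88.2). The errors run both ways.

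**3. What the discordant PCR can show.** Among infected patients, concordant pairs add equally to both assays. The sensitivity difference is therefore (b − c) / D, where b and c are the PCR-positive A+I− and A−I+ counts. Exact two-sided McNemar:

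- Error-free Accula: 10 v 0, p = 0.002.
- 80% v 75%: independent 8 v 6, p = 0.79 (8/14 = 57.1%, exact 95% interval 28.9% to 82.3%); midway 5 v 3, p = 0.73; nested 2 v 0, p = 0.50.
- Smallest one-sided split below 0.05: 6 v 0, p = 0.031 (5 v 0 gives 0.063).

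If Accula sensitivity is 95%, misses are independent and every discordant pair is verified, power against ID NOW at 70% / 80% / 90% is 0.34 / 0.09 / 0.004 with 20 infected, 0.62 / 0.25 / 0.02 with 30, and 0.90 / 0.52 / 0.07 with 50.

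**4. Unverified pairs.** Take the independent case, 8 v 6, and allow specificity below 100%, so that an unverified pair may be infected or not. Accept the enrolling PCR, so that pairs go unverified only among patients with a rapid-test order.

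- No infected patient enrolled through PCR and half the pairs unverified (4 and 3): bounds are 8 v 3 (p = 0.23) to 4 v 6 (p = 0.75). The direction can reverse.
- 20 of 40 enrolled through PCR and no rapid-order pair verified: the same bounds.
- 30 of 40 enrolled through PCR and no rapid-order pair verified: by proportion 2 and 1.5 expected pairs are unverified, and the worst case is 6 v 6 (p = 1.00). The direction does not reverse.

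**The case against.** The strongest defence is that this is a method comparison. Purpose accepts a comparable result as well as a superior one, Methods speaks of correlation, and agreement with the assay in use is a legitimate output. That stands for agreement figures under that name. But the plan names sensitivity, specificity, PPV and NPV and predicts similar or superior values, and a better Accula would also look less comparable on these figures.

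Second, PCR is not idle: it has a confirming purpose and is recorded. That is true, but confirming a result is not an analysis, and no estimate uses it.

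Third, PCR on discordant pairs alone cannot give unbiased absolute sensitivity or specificity, and power is low. Both points stand and limit what can be claimed. Neither invalidates the paired comparison.

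Fourth, patients enrolled as PCR-positive are a richer source, because both assays can be set against PCR there, concordant negatives included. They can inform only sensitivity, and their number shifts the agreement figures: in the independent 80% v 75% case, negative agreement is 97.8%, 88.6% and 78.2% with 10, 40 and 60 infected of 100. This is a useful addition and one more reason not to read agreement as accuracy.

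**Conclusion.** The concern holds. That ID NOW scores 100% against itself, and that Accula can at best equal it, follows from the stated rule and needs no assumed figure. If ID NOW specificity is perfect, an error-free Accula's apparent PPV equals ID NOW's true sensitivity. The other sizes are illustrative: they rest on assumed infected share, sensitivities, perfect specificities (relaxed for the unverified pairs) and overlap of misses, none of which the plan gives. The paired comparison further assumes that PCR reflects infection status when the paired swabs were taken. It could reveal a large advantage for Accula, but would usually leave a modest one unresolved at 100 patients.

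**What to change.** 1. Relabel the four ID NOW-referenced figures as positive and negative agreement and the matching predictive agreement, with exact intervals (for example 27/30 = 90.0%, 73.5% to 97.9%). State that they are not accuracy, do not support superiority and depend on the enrolment mix.
2. Make the head-to-head comparison a table of discordant pairs by direction (Accula+/ID NOW−, Accula−/ID NOW+) and PCR result. PCR-positive pairs compare sensitivity and PCR-negative pairs compare specificity, with counts, exact intervals and exact McNemar tests. State that power is low and that at least 6 v 0 is needed for two-sided p < 0.05. Do not fold discordant-only PCR into sensitivity or specificity. Since no margin defines similar, report that as an estimate with its interval.
3. Report unverified discordant pairs by direction, with best-case and worst-case bounds that allow specificity below 100%.
4. Minor: record the PCR specimen date, or days from the paired swabs. Show the discordant table with and without PCRs outside a window that the sponsor sets in advance, for existing and new specimens alike.

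Useful additions are a split by enrolment route and a direct comparison of both assays in the patients enrolled as PCR-positive.

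The cost is analysis wording and one extra data field (PCR date or interval). The enrolling PCR result and enrolment route also need recording if they are not already kept. No swabs or patients are added. The downside is less flattering labels and a paired comparison that will often be inconclusive.

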Patients with orders for rapid COVID-19 testing who have consented to participate will be included in the study. We will also include patients who have been confirmed positive for COVID-19 by PCR, swabs will be collected from these patients after obtaining consent. For patients with orders for rapid COVID-19 testing, one additional clinical specimen, anasal specimen will be collected from the patient at the same time as the initial specimen for the ID NOW. For patients who were confirmed positive by PCR, two additional swabs will be collected: one for the ID NOW and one for the Accula test. Swabs for both ID NOW and Accula testing will be provided to the clinical teams in pre-packaged kits with directions on specimen collection and transport. After collection, all swabs must be labeled with a specimen label (per current protocol). Following consent and collection of specimens, specimens will be sent to the microbiology laboratory. The ID NOW COVID-19 assay will continue to be performed STAT.

If laboratory testing personnel are available, the additional swab will be eluted in a buffer tube as recommended by the manufacturer and then utilized for the Accula SARS-CoV-2 assay. In the event that immediate testing cannot be performed, however, swabs will be stored at room

temperature for two hours or 2-8°C for up to 24 hours prior to testing on the Accula (per manufacturer's guidelines). The Accula system is a new platform for the microbiology laboratory. The manufacturer of the Accula Test, Mesa Biotech, has been working in conjunction with the National Ascension Laboratory team to pilot this study in two Ascension Markets (Michigan and Florida). Five Accula analyzers will be sent to the Ascension Michigan Clinical Microbiology Laboratory along with SARS-CoV-2 test kits. The protocol for testing will strictly follow the manufacturer's instructions (https://www.fda.gov/media/136355/download).

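### Accula PPV and NPV come straight from a study table whose positive share is an artificial mix, so they may not hold where prevalence differs

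*Combined protocol and SAP*

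**What the plan says.** The analysis is one sentence at the end of Data Management and Analysis. It takes the ID NOW as comparator and names four measures for the Accula: "sensitivity, specificity, positive-predictive value, negative predictive value". It gives no positive rate, no recalculation at other rates, no split by recruitment route and no confidence intervals. Predicted Results then expects the Accula to match or exceed the ID NOW on all four measures, so PPV and NPV are part of the predicted result.

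The sample has two sources, both described in Methods. The first is the hospital's own emergency department patients and inpatients with rapid orders: "Currently when rapid COVID-19 tests are ordered on ASJ ED patients or inpatients one nasal swab is collected by the clinical staff". The second is known positives: "We will also include patients who have been confirmed positive for COVID-19 by PCR, swabs will be collected from these patients after obtaining consent". Neither the number nor the share of the second group is stated. Sample Size and Duration of Study says only "The aim is to test 100 unique patients", expected within about a week.

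The Purpose says that, if the Accula is comparable or better, "then this assay may potentially be used throughout Ascension, especially in markets which have limited access to testing", and it names restarting elective surgery as a benefit. The Background describes the ID NOW in words only: "While this assay has a high positive predictive value, the sensitivity and negative predictive value are low".

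**The concern.** Sensitivity and specificity condition on the comparator result. PPV and NPV condition on the Accula result, so they also carry the proportion of positives in the table. Two features of this plan make that matter.

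First, the proportion of positives is set partly by how many PCR-confirmed patients are recruited. That is a recruitment choice, not a property of any population.

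Second, the settings named in the Purpose include patients who may differ from emergency and inpatient rapid-order patients at one hospital, such as those tested before elective surgery. Dropping the PCR-confirmed patients deals with the first feature and not the second.

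At stake is how the two figures are read outside the study. At a lower positive rate, a larger share of Accula positives would be unconfirmed by the comparator than the study reports. At a higher rate, a larger share of Accula negatives would be comparator-positive.

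**Working it through.** **Inputs.** The only numerical design figure is 100 patients. It comes with no precision target, power or prevalence, so there is no planned figure to reproduce. Sensitivity (Se), specificity (Sp), the positive rate p and the number k of PCR-confirmed patients are all assumptions here, shown as ranges. Positive means positive on the comparator.

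**Formulas.**
- PPV = Se·p / [Se·p + (1−Sp)(1−p)]
- NPV = Sp(1−p) / [Sp(1−p) + (1−Se)p]
- Positive share with k PCR-confirmed patients among 100 = [k + (100−k)p] / 100, assuming they are still positive on the ID NOW

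**Step 1: effect of the added positives.** Take Se 90%, Sp 98% and 10% positive among rapid-order patients.

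| k | Positive share | PPV | NPV |
|---|---|---|---|
| 0 | 10% | 0.090/(0.090+0.018) = 83.3% | 0.882/(0.882+0.010) = 98.9% |
| 20 | (20+8)/100 = 28% | 0.252/(0.252+0.0144) = 94.6% | 0.7056/(0.7056+0.028) = 96.2% |
| 50 | (50+5)/100 = 55% | 0.495/(0.495+0.009) = 98.2% | 0.441/(0.441+0.055) = 88.9% |

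The assay is the same in each row; only recruitment changes.

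**Step 2: rapid-order patients only (k = 0), different settings.** Again Se 90%, Sp 98%.

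| p | PPV | NPV |
|---|---|---|
| 40% | 0.360/(0.360+0.012) = 96.8% | 0.588/(0.588+0.040) = 93.6% |
| 20% | 0.180/(0.180+0.016) = 91.8% | 0.784/(0.784+0.020) = 97.5% |
| 5% | 0.045/(0.045+0.019) = 70.3% | 0.931/(0.931+0.005) = 99.5% |
| 1% | 0.0090/(0.0090+0.0198) = about 31% | 0.9702/(0.9702+0.0010) = 99.9% |

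From 40% to 5%, the unconfirmed share of Accula positives rises from 3.2% to 29.7%.

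**Step 3: dependence on the assumed accuracy.**
- Se 90%, Sp 95%: PPV is 0.360/(0.360+0.030) = 92.3% at 40% and 0.045/(0.045+0.0475) = 48.6% at 5%.
- Se 95%, Sp 99%: PPV is 98.4% at 40% and 83.3% at 5%.
- Se 95%, Sp 100%: PPV is 100% at every rate. NPV still moves, from 99.7% at 5% to 95.2% at 50%.

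**Step 4: would a confidence interval cover it?** With 100 patients, 30% positive, Se 90% and Sp 98%, expected counts are close to 27 true and 1 false positive, 69 true and 3 false negatives. Wilson 95% limits are 82.3% to 99.4% for PPV (27/28) and 88.5% to 98.6% for NPV (69/72). The PPV of 70.3% at a 5% rate lies below that lower limit. An interval on the raw value describes sampling error at the study's own mix and says nothing about transfer to another setting.

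**The case against.** The strongest case against is that this is a general caution about any diagnostic study. The Purpose speaks only of possible use, names sensitivity alone among the parameters, and nowhere claims that the study's PPV or NPV will apply elsewhere. Each patient has both tests, so the in-study comparison is paired. The obvious remedy, a prevalence grid for both assays, cannot be built. The ID NOW is the comparator, so its own sensitivity and specificity are not estimated, and Methods plans confirmatory testing only for discrepant pairs, where possible. Even an Accula grid would predict the ID NOW result, and the Background itself describes that assay's sensitivity as low.

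Much of this stands, and it limits the point. A reader might infer any of four stronger claims, none of which the documents support:

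- That the figures will be wrong elsewhere. No prevalence is given for any site. The shift would be nil at equal rates, and PPV would not move with perfect specificity.
- That the figures reflect this hospital's own prevalence. As written, the added PCR-confirmed patients make the mix artificial.
- That the intended use is other markets only. The text covers all of Ascension, with emphasis on limited-access markets, and so includes the home system.
- That the roll-out decision rests on PPV and NPV, or that raw Accula values will be set beside the Background's description of the ID NOW. Neither is stated.

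What the objection does not remove is that both values are named outputs and part of the predicted result, with no statement of the positive rate to which they belong. The planned analysis also yields no ID NOW predictive values against which that prediction could be judged.

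**Conclusion.** The point holds in a limited form: the planned PPV and NPV describe this sample's mix and may not carry over to settings with a different positive rate, and analysing rapid-order patients alone would not change that. The size depends wholly on assumed inputs. Between positive rates of 40% and 5%, PPV falls by 26.5 percentage points (96.8 − 70.3) at specificity 98%, by 43.7 (92.3 − 48.6) at 95%, by 15.1 (98.4 − 83.3) at sensitivity 95% and specificity 99%, and by nothing at 100%. The calculations hold sensitivity and specificity constant across settings, which is itself an assumption when the comparator is imperfect. This is a reporting and interpretation weakness that should be corrected before the analysis; it does not invalidate the paired comparison.

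**What to change.** In Data Management and Analysis:

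1. Make positive and negative agreement of the Accula with the ID NOW, each with a 95% confidence interval, the basis of the conclusion, and align Predicted Results with this.
2. Report raw PPV and NPV for rapid-order patients only, with their positive rate beside them, as a description of this sample.
3. If predictive values are to support wider use, tabulate Accula PPV and NPV over a fixed grid of ID NOW positive rates (for example 1, 2, 5, 10, 20 and 40%), with limits carried through from the agreement intervals. Label the table as predicting the ID NOW result, not infection, and state that agreement is assumed constant across settings.
4. Do not compare PPV or NPV between the two assays unless both are estimated against a common reference and at the same prevalence. The planned data do not provide this for concordant rapid-order patients.

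Cost: one extra table, confidence intervals that the plan does not now include, and a recruitment-route field, since the described spreadsheet entries do not name one. No further specimens are needed for items 1 to 3. The downside is that PPV at low positive rates will look less favourable and its limits will be wide.

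### With ID NOW as the only comparator, the planned analysis cannot show Accula superior on sensitivity, and no confidence intervals are planned

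*Combined protocol and SAP*

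**What the plan says.** Data Management and Analysis ends with the only statement of the accuracy analysis: "The following test parameters for the Accula will be calculated using the ID NOW as a comparator". It lists sensitivity, specificity, PPV and NPV. Background says of ID NOW that "the sensitivity and negative predictive value are low". Purpose sets the aim: "If the Accula system is comparable or demonstrates superior test parameters including sensitivity, then this assay may potentially be used throughout Ascension". Predicted Results expects all four parameters to be similar or superior to ID NOW.

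Patients enter by two routes. Besides patients with a rapid-test order, Methods states: "We will also include patients who have been confirmed positive for COVID-19 by PCR". For that second group, "two additional swabs will be collected: one for the ID NOW and one for the Accula test". Rapid-order patients give one extra swab. Neither route has a number. Sample Size and Duration of Study says only: "The aim is to test 100 unique patients".

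When the two assays disagree, Methods provides for a further specimen, if one can be obtained, "to confirm the COVID-19 results (unless the PCR results are already available"). Any Roche or send-out result goes into the study spreadsheet, but no stated analysis uses it. On other data fields: "The only patient demographic information that will be recorded in the spreadsheet is the specimen barcode number for the ID NOW".

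**The concern.** The calculation does not match the question. A comparison meant to reveal a more sensitive assay is referenced to the assay whose sensitivity the plan itself calls low. Where Accula finds an infection that ID NOW misses, the calculation penalises Accula, so a better assay can look less specific. Sensitivity is the one parameter that Purpose names when it discusses possible wider use, so the figure informing that decision could not show the advantage being looked for.

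The second part is precision. The denominator of the planned sensitivity is the number of ID NOW positives, not 100. That number is not fixed and no interval is planned, so a reader of the result could not tell a firm 90% from a loose one.

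**Working it through.** **Reproducing the plan's figure.** The 100 can be neither reproduced nor refuted. The document gives no alpha, power, margin, expected sensitivity, prevalence or precision target.

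**The ceiling.** Let a = both positive, b = Accula only, c = ID NOW only, d = both negative. The planned parameters are:
- sensitivity a/(a+c)
- specificity d/(b+d)
- PPV a/(a+b)
- NPV d/(c+d)

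Replace Accula by ID NOW itself and b = c = 0, so all four equal 100%. No Accula result can exceed that. Infections found only by Accula enter b, which lowers specificity and PPV and never raises sensitivity.

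**Example 1 (assumed counts).** Of 50 PCR-confirmed patients, Accula detects 50 and ID NOW 40, so a = 40, b = 10, c = 0, d = 0.
- Planned sensitivity: 40/(40+0) = 100%, a tie.
- Planned PPV: 40/(40+10) = 80%.
- If the other 50 patients are negative on both assays, planned specificity is 50/(50+10) = 83.3%.
- Paired difference in detection: (b−c)/n = (10−0)/50 = +20 points; Tango score 95% CI 11.2 to 33.0.

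**Example 2 (assumed).** 50 of 100 patients are infected; true sensitivity is 75% for ID NOW and 90% for Accula, with independent errors and no false positives.
- a = 50×0.75×0.90 = 33.75
- c = 50×0.75×0.10 = 3.75
- b = 50×0.25×0.90 = 11.25
- d = 100−33.75−3.75−11.25 = 51.25
- Planned sensitivity 33.75/37.5 = 90%; specificity 51.25/62.5 = 82%; PPV 33.75/45 = 75%.

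A true 15-point advantage is reported as 90% against a reference that is 100% by construction.

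**Precision by number of positives.** Exact (Clopper-Pearson) 95% intervals at 90% observed:

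| Positives | Detected | 95% CI |
|---|---|---|
| 10 | 9 | 55.5-99.7% |
| 20 | 18 | 68.3-98.8% |
| 30 | 27 | 73.5-97.9% |
| 40 | 36 | 76.3-97.2% |
| 50 | 45 | 78.2-96.7% |

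**How likely are few positives?** With k PCR-confirmed patients among the 100, ID NOW positives are Bin(k, s) + Bin(100−k, s × prevalence). Here s is ID NOW's detection rate, assumed to be 80%, with no false positives. The chance of 20 or fewer is:

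| k | Prevalence 10% among rapid orders | Prevalence 20% |
|---|---|---|
| 0 | over 99.9% | 89% |
| 10 | 96% | 31% |
| 20 | 27% | 1.1% |
| 30 | 0.2% | under 0.1% |

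The answer runs from near certainty to near zero, depending on two quantities that the document does not give.

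**The case against.** **Comparability is also an aim.** Purpose accepts comparable performance as well as superior, and agreement with ID NOW can be assessed as planned. This stands: the study is not defeated, and a reader who inferred that it cannot meet its purpose at all would go too far.

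**PCR information exists.** Every PCR-confirmed patient has a PCR result, and discordant pairs get a more sensitive test. This narrows the gap to the analysis, because the data for a fair comparison are partly in hand. It does not close the gap. Confirmation of discordant pairs depends on obtaining another specimen, and no stated calculation uses any PCR result.

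**The plan enriches for positives.** A reader might infer from the 100 that the study will end with too few positives. The document does not support that: it says PCR-confirmed patients will be included, and 20 or 30 of them can make the risk small. Few positives is a case the plan does not exclude, not the expected result.

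**A fixed minimum of PCR-confirmed patients has real costs.** A reader might conclude that the plan needs one, such as 50. That number would rest on a precision target the document does not set. Within 100 patients, each place moved to that route adds one study swab and one ID NOW test: 50×2 + 50×1 = 150 study swabs, against 100×1 = 100 if all were rapid orders. Background says ID NOW kits are in limited supply. The move also thins the other route: 50 rapid orders at an assumed 10-20% prevalence and 80% detection give 50×0.10×0.80 = 4 to 50×0.20×0.80 = 8 ID NOW positives. Even with perfect agreement, the exact lower limits are 39.8% (4/4) and 63.1% (8/8). This objection stands, and no minimum is proposed.

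**Conclusion.** The comparator problem is an error in the plan as written. It follows from the definition of the parameters and needs no assumption about prevalence or true accuracy: an analysis referenced only to ID NOW cannot show superiority to ID NOW. The size of the distortion does depend on assumptions; in the two examples PPV falls to 80% and 75% although Accula has no false positives.

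The absence of planned confidence intervals is a genuine omission. Precision on sensitivity is uncertain rather than shown to be poor, because enrichment makes few positives less likely but guarantees no number. The target of 100 is unjustified, not shown to be wrong.

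**What to change.** 1. In the PCR-confirmed patients, prespecify the paired Accula minus ID NOW difference in detection, with a score 95% CI, as the comparison that addresses superior sensitivity. Both swabs are already planned for this group. Give each assay's detection rate with an exact 95% CI, and call it sensitivity only where the qualifying PCR is close in time, by an interval the sponsor sets beforehand.
2. Label the ID NOW-referenced figures positive and negative percent agreement. Report them by recruitment route, with their denominators and exact 95% CIs.
3. Report PPV and NPV from rapid-order patients only, stating that ID NOW is the reference. Adding known positives changes the share of positives and so distorts both.
4. Add recruitment route and qualifying-PCR date to the spreadsheet, and amend the sentence in Data Management and Analysis that limits what is recorded.

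**Cost.** Two spreadsheet columns and a short analysis paragraph; the total stays at 100, and no swab or test is added beyond those planned. Intervals by route will be wider than pooled ones. Known positives may differ in spectrum from presenting patients, and some may have cleared virus since their PCR. The report should state both limits.
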